6.1.4 Emotion Assessment

Emotions are inevitably linked to the occurrence of expected and unexpected death while treating a patient or patient simulator.¹⁶ As these feelings may foster or impair the learning effect, emotions that occurred throughout the simulation scenarios will be assessed. Participants will be asked to classify their emotions they experienced throughout the study by using the established Positive and Negative Affect Schedule (PANAS) at the end of each scenario. This assessment will be done immediately after debriefing of the respective scenarios.

6.1.5 Survey

Following each scenario and completion of risk assessment, participants will be interviewed to determine their subjective views of their decision-making and performance. In order to contextualize the effects of simulated death, an open ended orally administered survey will follow the retention test phase (see Appendix E) for all subjects. The orally administered surveys will be approximately 30 minutes in length and will be recorded for transcription. Transcripts will be anonymized. This open-ended survey is intended to provide basic contextual information, thus data will be analyzed using inductive thematic analysis²⁹⁻³¹ to create general themes. Analysis will be guided by a Research Associate with specialized qualitative research training. Findings from the qualitative component will help to inform directions for future research.

6.1.6 Debriefing Assessment

In order to assess the debriefing quality and avoid potential bias by inconsistent quality, all debriefings will be video recorded and rated by two independent expert raters using the validated 8-item 5-point OSAD scale.³² Again, the raters will be intensively trained in using the scale prior to the start of the study.

6.2 Randomization

In order to create groups of participants that are similar in regards of their baseline characteristics and in order to increase the power of our study we will use the approach of stratified randomization to allocate the participants to the intervention and control group. In order to keep the number of strata and the resulting covariates small we will stratify the participants regarding their level of training (PGY1 – PGY3 residents, vs. PGY4 – PGY 5 residents and fellows), their likelihood of providing acute care (acute care specialties will include anesthesia, emergency medicine and critical care trained personnel). Thereafter computer block randomization will be performed using the algorithm provided at www.randomization.com for all subgroups. Participants will be assigned to the

intervention (initial test ending with asystole) and control (initial test ending with sinus rhythm) groups in a 1:1 ratio. To ensure even allocation to the intervention and control group blocks of 4 participants will be predefined. Sealed, numbered, opaque envelopes, containing the random allocation, will be opened after the resting period immediately before scenario briefing begins.

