5.1.2 Inclusion criteria

Participants will be enrolled after approval of the respective site coordinator. Participants are required to refrain from physical strains, smoking, drinking caffeinated or low pH beverages and

eating for at least one hour before enrollment. Furthermore participants will be included between 11 AM and 8 PM, when cortisol levels are most stable.

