6.3 Blinding

Investigators performing data analysis and video raters will be blinded to group allocation by editing audio/video material in such a way that the final end of the scenario, with the occurrence of death or return of spontaneous circulation is not visible. Participants will be blinded to the nature of the study, their group assignment and scenario at the time of enrollment and scenario briefing during the initial and retention test.

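### A single fixed block size of 4 in every stratum lets anyone who tracks a stratum know up to about a third of allocations in advance; vary the sizes and keep them undisclosed (minor, cheap improvement)

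*Protocol*

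**What the plan says.** Protocol 6.2 forms four strata from two binary factors: junior or senior training level, and acute-care or other specialty. Site is not named as a factor. Within the strata, "Thereafter computer block randomization will be performed using the algorithm provided at www.randomization.com for all subgroups". The arms are "groups in a 1:1 ratio", and one block size is given: "To ensure even allocation to the intervention and control group blocks of 4 participants will be predefined". Concealment rests on this sentence: "Sealed, numbered, opaque envelopes, containing the random allocation, will be opened after the resting period immediately before scenario briefing begins".

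On blinding, Protocol 6.3 covers two sets of people. The first is analysts and raters: "Investigators performing data analysis and video raters will be blinded to group allocation by editing audio/video material". The second is participants: "Participants will be blinded to the nature of the study, their group assignment and scenario at the time of enrollment and scenario briefing". Session staff are not listed. Protocol 6 (Retention Test, Both Phases) puts two confederates in the room and an operator at the mannequin, and 6.4.2 has the debriefer discuss the death with the participant. All of them learn the ending, which in the initial test is the allocation.

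On entry to the trial, Protocol 5.1.1 describes personal invitations by email and phone, and 5.1.2 adds a gatekeeper: "Participants will be enrolled after approval of the respective site coordinator".

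Neither document says who generates the list, who holds or opens the envelopes, whether lists are kept by site, or whether the block size is withheld from anyone.

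**The concern.** An opaque envelope hides an allocation only if the allocation cannot be worked out from earlier ones. In a block of four with two per arm, once two participants have gone to the same arm, the rest of the block is fixed. Both stratifying factors are facts that can be known about a trainee before booking. Participants are tested individually, so endings become known one at a time and in order.

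At stake is selection within a stratum. Someone who knows that the next slot is a death slot could approve, invite or schedule a particular trainee for it. The ANCOVA in Protocol 7.3 and in the SAP (Primary Outcome) adjusts for the two stratifying factors only, so a difference in ability or resilience inside a stratum would not be adjusted for. Blinded rating of edited video does not undo a group difference created at entry.

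**Working it through.** **Inputs.** Block size 4, 1:1, separate blocks per stratum, four strata (Protocol 6.2). Total recruited 56 (Protocol 7.2). The split of 56 across strata is not given, so several splits are shown.

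**The plan's own figure.** The documents give no figure for predictability; the one figure used here is the sample size. A two-sided t-test with d = 0.8, alpha 0.05 and power 0.80 needs 52 in total. Then 52 × (1 − 0.12) = 45.76, so 46, and 46 × 1.2 = 55.2, so 56. Both stated numbers reproduce.

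**Certain allocations in one block.** Write D for death and S for survive. An allocation is certain if the earlier ones in the block have already used up one arm.

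| Sequence | Positions known in advance | Count |
|---|---|---|
| DDSS, SSDD | 3 and 4 | 2 each |
| DSDS, DSSD, SDSD, SDDS | 4 only | 1 each |

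Mean per block = (2 × 2 + 4 × 1)/6 = 1.33, and 1.33/4 = 33.3%. By position, the chances of certainty are 0, 0, 1/3 and 1.

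**Applied to 56 participants.** An incomplete last block lowers the share, because its early positions are never certain.

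| Split (assumed) | Certain allocations | Share |
|---|---|---|
| 20/16/12/8, all blocks complete | 56 × 1/3 = 18.7 | 33.3% |
| 25/15/10/6 | 16.3 | 29.2% |
| Four strata of 14 | 4 × (3 × 1.33 + 0 + 0) = 16.0 | 28.6% |
| Lists also split by site, 8 cells of 7 | 8 × (1.33 + 0 + 0 + 1/3) = 13.3 | 23.8% |

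**One list shared by two sites.** Assume each participant is equally likely to attend either site, the position in the block is known, and the sites exchange nothing. Position 3 is certain only if one site saw both earlier endings and they matched: 1/4 × 1/3 = 1/12. Position 4 is certain only if that site saw both members of the arm already used up: 1/4. The share is (1/12 + 1/4)/4, about 8%.

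**Best guess.** In a complete block of 4 the chance of guessing correctly is 1/2, 2/3, 2/3 and 1 by position, a mean of 2.83/4 = 70.8% against 50% by chance. Over a stratum of 14 it is (3 × 2.83 + 1/2 + 2/3)/14 = 69%.

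**Varying the block size.** These values come from 4,000 simulated strata of 14, with hidden sizes, each equally likely, and an optimal guesser.

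| Block sizes | Certain | Best guess correct |
|---|---|---|
| Fixed 4 | 28.6% | 69% |
| 4 or 6 | about 6% | 68% |
| 4, 6 or 8 | about 2% | 67% |

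For 56 participants, 6% is 0.06 × 56, about 3 certain allocations instead of 16.

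**The case against.** - **Staff blinding.** A reader might infer that blinding of staff fails. The plan does not claim it: Protocol 6.3 names analysts, raters and participants only. The operator must deliver the assigned ending and so has to know the arm whatever the block size, and nothing withholds it from the confederates once the envelope is open. Any concern about staff behaving differently during the scored part comes from unblinded staff rather than from blocks of 4, and varied blocks would not change it. This objection stands in full.
- **Who could use the knowledge.** A reader might infer that concealment fails outright. That needs the people who approve or book participants to know the block size and the past endings. The documents do not show that site coordinators attend sessions, that one team covers all sessions or both sites, or that staff had the protocol during recruitment. This stands as a limit on the claim, although the documents do not separate these roles either.
- **Effect on the primary outcome.** A reader might infer that the main contrast is biased. No size or direction can be derived. Protocol 7.1.1 defines the outcome as a change between tests, so selection on stable ability would partly cancel. The SAP lists total score as the dependent variable, and there the cancellation would not apply if retention scores were analysed alone. Bias is possible but not shown.
- **Small gain in guessing.** Best-guess accuracy falls by about one percentage point. That is correct; the gain lies in removing certainty.

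**Conclusion.** The point holds as a weakness in concealment at the approval and booking stage. Up to about one third of allocations are knowable in advance: 33% with complete blocks, 28.6% with 14 per stratum, and about 24% with lists split by site. The first is a ceiling. All three assume an observer who knows the block size and sees every earlier ending in the stratum. With one list across two sites that do not share information, the figure is about 8%.

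The documents leave this route open but do not show that anyone is placed to use it. They support neither a failure of concealment nor a breach of staff blinding. Severity is minor; the change is worth making because it costs almost nothing.

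**What to change.** In Protocol 6.2:

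- Replace the single block size with randomly varying sizes (for example 4 and 6) within each stratum. State in the protocol only that sizes vary, and record the sizes in a separate document not available to session staff or site coordinators until recruitment closes.
- State that the list is generated and held by someone who does not recruit, approve, book or run sessions.
- State who holds and opens the envelopes, and whether lists are kept by site.
- Confirm that the web tool named there can produce mixed block sizes.

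**Cost.** A short protocol edit and a regenerated list before first enrolment. If a last block is left incomplete, imbalance within a stratum can reach 3 instead of 2, so at worst 12 instead of 8 over four strata. The stratifying factors are already covariates in the ANCOVA. The change does not affect what staff know once the envelope is opened.

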6. METHODOLOGY

Institutional ethics approval will be sought from the Ottawa Hospital Research Ethics Board and the University of Toronto Research Ethics Board for Health Sciences. Informed consent and a confidentiality agreement will be obtained from participants. Participants will be enrolled after approval from their resident site coordinator. They are asked to refrain from physical strains, smoking, drinking caffeinated or low pH beverages and eating for at least one hour before participating. The trial will be conducted between 11 AM and 8 PM to warranty stable cortisol levels. All participants will be asked to switch off their mobile phones and pagers in order to prevent distraction during the study.

Initial Test

After a standardized accommodation phase of 15 minutes, all participants will be exposed to a prerecorded, 15 minute long video-review of the actual advanced cardiac life support algorithms. We will collect baseline data including demographic data, stress markers and data on anxiety thereafter as described below.

Immediately before a short scenario briefing the participants will be randomized to either the intervention (unexpected death) or control (survive) group. Participants from both groups will have to individually manage a simulated in-hospital cardiac arrest scenario as team leader (Appendix C). At the initial test, in the intervention group (unexpected death), the scenario will be designed to ultimately lead to the death of the simulation mannequin, regardless of the participant's performance. In the control group (survive), the mannequin will survive. We will attempt to ensure that participants do not anticipate the series of events in the retention resuscitation scenario based on their experience during the initial resuscitation scenario (recall bias). Therefore, the scenarios will be different in terms of order of the presenting arrhythmia. For example the participant who manages a patient with ventricular fibrillation (VF), then pulseless electrical activity (PEA), followed by asystole in the initial scenario will go on to manage a patient with pulseless electrical activity (PEA), then ventricular fibrillation (VF), then return of spontaneous circulation (ROSC) in the retention test. The clinical stems of the scenarios in the initial test versus the retention test will also

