Following the retention scenario and completion of risk assessment, participants will be interviewed to determine their subjective views of their decision-making and performance within an orally administered survey approximately 30 minutes in length.

Both Phases

The setting and equipment will be the same in the initial and the retention phase, reflecting an appropriately equipped normal ward room at our hospital. SimMan (Laerdal, Stavanger, Norway) will be used as the standardized simulation mannequin in all scenarios. The mannequin will be placed in a patient bed. The mannequin will be operated by an experienced simulation specialist from a separated control room. All scenarios will be peer reviewed and validated by experts in the field of medical simulation and resuscitation. The scenarios will be prescribed for a duration of maximum 15 minutes. The confederates acting as team members during the scenarios will receive extensive precourse training with prescribed responses and interactions. Predefined, peer reviewed cues will be given by the supporting staff in case the participants fail to recognize the cardiac arrest situation. These cues will include the repetition of the case presentation and vital parameters.

Each phase is accompanied by assessment of baseline data, stress parameters and emotions. All scenarios and debriefings will be video recorded to allow performance assessment by two independent experts raters blinded to group allocation.

In order to collect meaningful qualitative data from a maximum of subjects, all subjects will be exposed to unexpected death either during their initial or retention scenario. Subjects of group “unexpected death” will have their simulated patient survive during the retention test while subjects from the group “survive” will have their patient die during the retention scenario. The course of both

subsets of scenarios is the same up until the final two minutes, and the final outcome of the scenarios will not be seen by the expert raters. Therefore, we do not consider this trial as a crossover design.

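### The allocation envelope is opened before the scored part of the initial scenario, although the arms diverge only in the last two minutes, and session staff are not among those blinded

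*Protocol*

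**What the plan says.** - **Timing of allocation.** Protocol section 6 (Initial Test) states: "Immediately before a short scenario briefing the participants will be randomized to either the intervention (unexpected death) or control (survive) group". Section 6.2 agrees: the envelopes, "containing the random allocation, will be opened after the resting period immediately before scenario briefing begins".
- **Where the arms part.** Section 6 (Both Phases) says the course of both "subsets of scenarios is the same up until the final two minutes", and that raters will not see how the scenario ends. On length: "The scenarios will be prescribed for a duration of maximum 15 minutes".
- **Who is blinded.** Section 6.3: "Investigators performing data analysis and video raters will be blinded to group allocation by editing audio/video material". Participants are also blinded at enrolment and briefing. No other role is listed, and no section says who opens the envelope or who is told its content.
- **Who is active during the scenario.** Two confederates carry out tasks when directed, and a simulation specialist runs the mannequin from a separate control room. "Predefined, peer reviewed cues will be given by the supporting staff in case the participants fail to recognize the cardiac arrest situation".
- **What is scored.** Section 6.1.2 uses the Ottawa Global Rating Scale and a task checklist. Post-resuscitation care is left out of the checklist to protect blinding.
- **Primary outcome.** Section 7.1.1 defines it as the difference between initial and retention performance, compared between arms.

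**The concern.** Blinding the raters protects the scoring of a performance, not its production. The primary scale covers leadership, communication and use of resources, which a team leader shows through dealings with the confederates. If a confederate, a cue-giver or the operator knows that this patient is scripted to die, help, cues or pace may differ by arm without anyone intending it. A blinded rater would then faithfully record a difference that staff had created.

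The initial score is one of the two components of the change outcome. If it is produced before anyone in the session knows the arm, it is a true pre-allocation baseline and can differ between arms only by chance. As written, the plan gives up that property although, by its own account of the scenarios, it does not need to.

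**Working it through.** **1. Timeline.** At the maximum length the stretch common to both arms is 15 − 2 = 13 minutes. The envelope is opened before the briefing, so the whole briefing and up to 13 minutes of scenario lie between opening and branch. The raters' material omits the ending. I take the cut to fall at or before the branch, since a later cut would show raters the arm. On that reading, everything scored lies inside this interval.

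**2. Roles against section 6.3.**

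| Role | Can influence the scored performance | Listed as blinded |
|---|---|---|
| Participant | produces it | yes |
| Video raters | score it | yes, by editing |
| Analysts | no | yes |
| Briefing staff | yes | no |
| Confederates | yes, within a script | no |
| Cue-givers | yes, predefined cues | no |
| Mannequin operator | yes, from the control room | no |

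**3. Route into the primary outcome.** Let change = retention − initial. If staff behaviour shifts the initial mean of one arm by *b* single-score SDs, the between-arm difference in change moves by the same raw amount. With equal variances and initial–retention correlation ρ, the shift in change-score SDs is *b* / √(2(1 − ρ)). Neither *b* nor ρ is in the documents. Taking *b* = 0.2 purely as an assumption:

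- ρ = 0.3: 0.2/1.183 = 0.17, or 21% of the design effect of 0.8
- ρ = 0.5: 0.2/1.000 = 0.20, or 25%
- ρ = 0.7: 0.2/0.775 = 0.26, or 32%

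**4. The plan's own figure, then an illustration.** Inputs from section 7.2: d = 0.8, two-sided alpha 0.05, power 0.8, r² = 0.12. A two-sample t-test needs 26 per arm, 52 in total. Then 52 × (1 − 0.12) = 45.76, rounded up to 46, as stated. The stated 56 follows from 46 × 1.20 = 55.2.

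Now let an assumed spurious shift, in SDs of the analysed outcome, act on 46 analysed participants in a four-parameter ANCOVA (42 df). The noncentrality is shift/√0.88 × √(46/4). For power, the shift is taken to oppose a true d of 0.8.

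| Assumed shift | Type I error | Power |
|---|---|---|
| 0 | 5.0% | 0.81 |
| 0.1 | 6.4% | 0.70 |
| 0.2 | 10.9% | 0.56 |
| 0.3 | 18.5% | 0.42 |
| 0.4 | 29.3% | 0.29 |

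This shows sensitivity to an assumed shift. It does not estimate what would happen in this trial.

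**5. Fixed blocks (side issue).** Section 6.2 says "blocks of 4 participants will be predefined". Of the six 2:2 orderings, the fourth allocation is always determined, and the third is determined in the two orderings whose first two allocations match (2/6 = 1/3). The deducible share is (1 + 1/3)/4 = 33%.

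**The case against.** The strongest objection is to the premise. Section 6 also says the scenarios differ in clinical context, first rhythm and outcome, and its worked example pairs a rhythm order with an ending. If stem or rhythm order is tied to arm, the allocation is needed at the briefing, which is when it is revealed. I read those differences as initial versus retention test rather than between arms, because the same section says the two courses coincide until the last two minutes. Appendix C would settle it and is not in the supplied text, so the reconciliation has to come first.

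Second, the safeguards are real. Confederates have prescribed responses, extensive training and an instruction not to advise. Cues are given only when the arrest is missed, and consist of repeating the case presentation and vital parameters. The operator sits apart. These measures limit how far staff could depart by arm. They are standardisation, not concealment, so they reduce the likely size of the bias without removing its source.

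Third, sealed, numbered, opaque envelopes opened after enrolment are a recognised way to conceal allocation at entry. That stands, but it guards against selective enrolment, not against staff knowledge during the scenario.

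Fourth, the 33% needs someone who knows the block size and follows every outcome within a stratum. The documents do not say whether lists are separate by site; with a shared list, staff at one site would see only part of the sequence. A reader might infer that a third of allocations are in fact known. The documents do not support that.

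**Conclusion.** The point holds as an open route to bias in the initial-test score that can be closed at little cost. It rests on three things: the common course up to the final two minutes, the absence of session staff from section 6.3, and the initial score entering the primary outcome as section 7.1.1 defines it. On the last, the SAP names the OGRS total score as the dependent variable. If only the retention score were modelled, the initial score would not enter the primary result.

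Three stronger readings go beyond the documents:

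- A reader might infer that staff are unblinded. The protocol says only when the envelope is opened, not who reads it, so knowledge of the arm is possible rather than shown.
- A reader might take 0.2 SD, or a quarter of the design effect, as the size of the bias. That shift is assumed, and its share of 0.8 depends on an unstated correlation.
- A reader might infer that later opening protects the whole primary outcome. The retention ending is always the reverse of the first, so staff who saw the first ending know the arm three months later, and the debriefer necessarily does.

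**What to change.** 1. **Reconcile first.** Check section 6 (Initial Test, Retention Test, Both Phases) against Appendix C, and state whether stem and rhythm order are independent of arm in the initial test.
2. **If they are independent,** have only the control-room operator open the envelope, at the branch point of the initial scenario. Amend sections 6 and 6.2 to match. State in 6.3 that briefing staff, confederates and cue-givers are unaware of allocation until then.
3. **If they are tied to arm,** restrict the allocation to the operator until the branch. Briefing staff would receive the stem, but not the ending paired with it. The initial score is then better protected, though not strictly pre-allocation.
4. **Retention test.** Where existing rosters allow, use confederates who did not attend that participant's initial session. Otherwise list this as a limitation in 8.2.
5. **Optional.** Use randomly varied block lengths within strata, not disclosed to session staff.

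The cost is an operator ready for either ending, a short protocol edit and a roster check. Item 5 adds a new list and slightly looser balance within strata. The 46 evaluable and 56 recruited, the alpha and the stated power stay as they are. The change should be made before recruitment, because initial scores already collected under the present procedure cannot be made pre-allocation afterwards.
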